8. SAFETY ASSESSMENT AND MONITORING

ADOPT PGx is a prospective, multicenter, subset analysis of 1:1 randomized Intervention (immediate PGx testing and genotype-guided opioid or SSRI therapy with clinical decision support) vs. Control (usual care with delayed PGx testing) pragmatic, open label clinical trial. It is regulated under an Abbreviated Investigational Device Exemption (IDE). The genotyping-guided therapy is the device and classified as a minimal risk to the welfare of the enrolled participants. Only Adverse Device Effect (ADE) events suspected to be related to the specimen collection, laboratory assay genotyping results, and phenoconversion recommendations from the Best Practice Alerts (BPAs)/Consult notes will be reported to the IRB. Reportable ADEs or unanticipated Adverse Device Effect (UADEs) events including unanticipated study related deaths will be collected in the study database per IRB reporting policies. See the MOP for more details.

The IRB reporting timeline requirements are:

- Immediately (within 24 hours) upon learning of an unanticipated study-related death. Study personnel will notify the IRB via phone or email by providing a brief summary of the event; then within 1 week (5 business days), study personnel should submit report to IRB
- Within 5 business days for unanticipated events
- Within 10 business days for any other problem or event

8.1 Medication Side Effects

Participant reported medication side effects will be collected in the baseline and follow-up surveys. The opioid medication side effects that will be surveyed include: problems with sleep; nausea, gas or indigestion; constipation or diarrhea; and dizziness or balance problems. The SSRI medication side effects that will be surveyed include: fatigue, change in weight, GI upset, sedation/somnolence, anxiety, insomnia, irritability/hostility, and sexual dysfunction.

8.2 Events of Interest

Participant reported emergency department visits and hospitalizations will be collected in the 1, 3, and 6-month follow-up participant surveys. EHR may be used as an additional source for emergency department visits and hospitalizations, up to approximately 12 months after the last patient is randomized, i.e. through completion of the 6 month-follow up activities. For the details of collecting EHR data, see Protocol section 7.8 and MOP. EHR results will be sent to the CC via secure data transfer and formatted for data analyses.

8.3 Data Safety Monitoring Board

The DSMB, appointed by the NHGRI, will be responsible for providing recommendations regarding the conduct of the study and guidance to ensure the safety and well-being of participants. The DSMB will meet semi-annually. A DSMB Charter will be developed detailing the procedures to be followed. A Data and Safety Monitoring Plan and a separate DSMB statistical analysis plan (SAP) will be developed in collaboration with the IGNITE PTN, IGNITE PTN CC, and NHGRI, and enacted by the DSMB.

8.4 Early Termination and Participant Discontinuation

Early termination considerations will generally apply only to emerging issues of major concern, or problems with trial conduct that suggest the trial could not be completed successfully with a reliable conclusion in a feasible time frame.

The site investigator, sponsor or institution may stop involvement of any participant in this research

study at any time without their consent. This may be because the research study is being stopped, the instructions of the study team have not been followed, the investigator believes it is in the participant's best interest, or for any other reason. If specimens or data have been stored as part of the research study, they too may be destroyed without participant consent.

9. MEDICARE AND MEDICAID CLAIMS DATA COLLECTION AND ANALYSIS

9.1 Rationale

The economic analyses will be conducted from the perspective of the payer with the primary goal to provide cost-effectiveness data that can inform reimbursement decisions for genotyping. Reporting metrics will include:

1. Average costs for each study arm, considering overall cost to the payer and select services directly relevant to the acute pain, chronic pain, and depression groups
2. Differences in cost utility between the intervention arm, considering overall cost to the payer and select services directly relevant to the acute pain, chronic pain, and depression groups
3. Incremental cost-effectiveness ratio (ICER), i.e., the incremental change in cost per unit improvement of effectiveness.

All metrics will be ascertained over a 6-month follow-up period with the assumption that beneficial effects of genotype-guided therapy are fully realized within this time period and that the control arm participants have not yet developed any cross-over effects from the 6-month delayed testing.

In a population of mixed payer types, collecting actual costs for all participants is not feasible. Therefore, costs will be obtained from Medicare and Medicaid claims data and imputed or cross-walked to the other payer types. Based on data in the National Inpatient Sample, 53% and 4% of knee and 59% and 4% of hip arthroplasties were reimbursed by Medicare and Medicaid, respectively. For chronic pain participants, data from the University of Florida suggest 40% and 20% are covered by Medicare and Medicaid, respectively. Thus, considering enrollment gaps, at least 60% of the study population is anticipated to have claims data, from which comprehensive cost analyses can be performed and extrapolated to the entire cohort. Major cost drivers associated with pain and depression will be ascertained from the participant using validated resource questionnaires, and verified through secondary claims data whenever possible.

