6.7 Costs to the Participants

The cost of clinical genotyping and collection of PRO outcomes will be covered by the clinical trial. The cost of their drug therapy will not be covered by the trial since they would be prescribed a medication regardless of participation in the trial. However, taking part in this study may lead to added costs to the participant, specifically the costs of their care, including the physician-prescribed drug therapy, which will generally be covered by the participant's insurance (if insured), and will not be covered by the study.

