9.2 Data Collection

Data for this specialized analysis will come from these sources:

1. Participant report of healthcare utilization (e.g. emergency department, urgent care, office) for all participants, these will focus on high-cost items and/or items that are expected to be sensitive to the intervention
2. Medicare claims data for Medicare enrollees
3. Medicaid claims data for Medicaid enrollees

Participant reported visits: Participant reported assessment for health care utilization is previously described in section 7.3.

Medicare claims data: For Medicare enrollees in fee-for-service (FFS) plans or Medicare Advantage, clinical groups will ascertain Medicare claims data (Part A-D) directly from the Centers for Medicare and Medicaid Services (CMS).

Medicaid claims data: For Medicaid enrollees, clinical groups will ascertain claims data from their states' Medicaid agencies directly.

To ensure full adjudication, requests to Medicare/Medicaid for claims data will be timed to occur between 6-12 months after the end of the 6-months follow-up of the last enrolled patient. Claims data will also be requested for one year before trial enrollment up to 6 months thereafter.

The procedure for obtaining claims data will require a database linkage step – mapping the participant study ID to the Medicare/Medicaid identifiers. The data linkage will rely on social security number (SSN) or Medicare ID and date of birth (DoB), which can be collected in two possible ways:

1. Both SSN and/or Medicare ID and DoB are collected as part of the trial by the recruiting site
2. One or both variables are extracted from the medical record of the participating health center by a healthcare data security officer or the local equivalent, on behalf of the study team

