For the Controls for Medicare and Medicaid beneficiaries, waiver of consent forms and HIPPA waiver of authorization will be obtained as the analyses of health care utilization and costs are retrospective in nature. It will be impracticable to obtain authorization from this population sample as patient contact information is unavailable.

Costs imputation

The Medicare/Medicaid (M/M) claims will be used to impute healthcare utilization and costs for participants who are enrolled in other plans or not insured as follows. First, the subset of the study participants with both the participant reported set of medical encounters and M/M claims data will be identified. In this subgroup, claims data and self-report data will be used to derive extrapolation factors for total healthcare utilization and cost across all study participants. Additionally, for participants in other plans or uninsured, we will use M/M data to assign average cost to each of the self-reported items.

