reasons, we will conduct covariate-adjusted repeated measures mixed models that will account for differences in baseline characteristics that differ between the Intervention – CYP2D6 PM or UM or CYP2C19 UM, RM or PM subgroup and the Control – CYP2D6 PM or UM or CYP2C19 UM, RM or PM subgroup. Potential baseline characteristics may include age, sex, income, education, insurance, medical conditions. We will select the appropriate covariance matrix (e.g. compound symmetry, autoregressive, unstructured, or other covariance structure) based on the data.

Difference within the NM group. In the control arm participants, we will compare depression scores and depression control in participants with a CYP2D6 activity score $>0.75 - 1$ to participants with an activity scores $>1-2$ using a two-sided two-sample t-test or Mann Whitney test, as appropriate, with a type 1 error of 0.05. Additionally, we will use linear regression to adjust for differences in baseline characteristics

Cost Effectiveness

Healthcare costs: In the Medicare fee-for-service or Medicaid enrollees, log-transformed overall expenditures (between index visit and 6 months follow-up) will be compared using a 2-sample t-test between the study arms (after ensuring that the variances in the log-scale are equal). Alternatively, cost comparisons will be made using appropriate regression models such as generalized linear models. For all participants, regardless of insurance type, we will estimate and aggregate participant-reported healthcare utilization during follow-up and assign cost for each item based on unit weighted mean cost estimates from the Medicare/ Medicaid data.

Within the Medicare/Medicaid population, we will compare estimated cost differences between genotype-guided and usual care based on billing records versus participant report to further validate the cost comparisons for the entire population. Cost for the index hospitalization for surgery participants will not be included in the cost estimate, but we will compare length of stay between groups as reference for hospitals regarding potential cost savings in capitation-based reimbursement schemes. All costs will be converted to 2021 \$US using the chain-weighted Consumer Price Index (CPI).

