Finally, we will compare the Medicare/Medicaid beneficiaries among our trial enrollees to a larger random sample of beneficiaries in the participating states and compare demographic and key clinical characteristics to explore representativeness of our study sample, evaluate the impact of attrition and loss to follow-up and make inferences about the generalizability of our results.

Cost utility: For the cost-utility analysis, the PROMIS-43 responses will be converted into utilities using previously validated crosswalks.[41] Cost and quality adjusted life year (QALY) estimates, adjusted for clustering within site and baseline utility for QALYs, will be obtained using appropriate regression models such as generalized linear models. The analysis of maximum likelihood parameter estimates will allow us to capture differences in cost and QALYs between the intervention arm and control arm of the trial. The Incremental cost-effectiveness ratio (ICER) will be calculated from costs and QALY. A bootstrapping approach will be used to characterize sampling uncertainty and calculate confidence intervals (CI) around the ICER estimate (2.5th and 97.5th percentiles corresponding to the lower and upper bounds of the CI, respectively). This sampling uncertainty will be summarized using cost-effectiveness acceptability curves.

Details of these statistical analyses, along with other exploratory analyses will be described in the study SAP.

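### As specified, the cost-effectiveness analysis leaves the price of the pharmacogenetic assay out of the intervention arm's payer cost, although its purpose is to inform reimbursement of that assay

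*Combined protocol and SAP*

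**What the plan says.** Section 9.1 adopts the payer's perspective and states that the main aim is to "provide cost-effectiveness data that can inform reimbursement decisions for genotyping". On inputs it says that "costs will be obtained from Medicare and Medicaid claims data and imputed or cross-walked to the other payer types". Metrics are taken over 6 months.

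Section 9.2 lists three data sources: Medicare claims, Medicaid claims, and "Participant report of healthcare utilization (e.g. emergency department, urgent care, office) for all participants". For participants without such claims, "claims data and self-report data will be used to derive extrapolation factors for total healthcare utilization and cost across all study participants".

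Section 10.6 (Healthcare costs) covers all participants by totalling self-reported utilization, and will "assign cost for each item based on unit weighted mean cost estimates from the Medicare/ Medicaid data". It excludes the index surgical hospitalization and sets 2021 US dollars as the price base. Under Cost utility, "The Incremental cost-effectiveness ratio (ICER) will be calculated from costs and QALY", with bootstrap intervals and acceptability curves.

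On the test itself, Section 6.7 says: "The cost of clinical genotyping and collection of PRO outcomes will be covered by the clinical trial". The same section says that the participant's care, including prescribed drugs, will generally fall to insurance. Section 7.5 has control samples genotyped only once the 6-month assessment is complete.

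**The concern.** A payer deciding whether to reimburse a test needs the test's price on the cost side. The plan's cost sources are defined closely enough to see what they can capture, and none of them can capture an assay paid from trial funds. The gap falls on one arm, so it does not cancel in the comparison.

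At stake is whether the arm cost comparison, the ICER and the acceptability curves answer the reimbursement question or a different one: whether testing is good value when the assay costs the payer nothing. A modest saving in claims could be reported as testing saving money, although the saving would not cover the assay.

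**Working it through.** The plan states no ICER, test price, expected cost difference or expected QALY difference, so there is no figure to reproduce. The check traces the cost sources and then works out the algebra.

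**1. Can any stated source contain the assay cost?**

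| Source | Where | Can it contain the assay? |
|---|---|---|
| Medicare and Medicaid claims | 9.1, 9.2 | Not expected: the trial pays (6.7) |
| Self-reported utilization | 7.3, Table 8, 9.2 | No: the items are care encounters such as emergency, inpatient and outpatient visits |
| Unit costs for self-reported items | 10.6 | No: they price only the items reported |
| Extrapolation factors | 9.2 | No: they are built from the sources above, so an item absent from both stays absent |

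No other rule in Section 9 or 10.6 adds a unit cost for the panel.

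**2. Does the omission cancel between arms?** No. Costs run over 6 months (9.1). Intervention samples are genotyped at the start, and control samples after the 6-month assessment (7.5). The correct within-horizon test cost is C per tested intervention participant and zero for controls. The plan's sources give zero for both.

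**3. Effect on the results.** Let ΔC be the incremental cost from the stated sources, ΔQ the QALY difference, and C the test price, with all intervention participants tested.

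- Incremental cost with the test: ΔC + C.
- ICER with the test: (ΔC + C)/ΔQ = ΔC/ΔQ + C/ΔQ. The ICER as written is therefore too low by C/ΔQ when ΔQ > 0.
- Net monetary benefit at threshold λ: λΔQ − (ΔC + C). As written, it is too high by C at every λ, whatever the sign of ΔQ. This is what moves the acceptability curves.
- If ΔC lies between −C and 0, testing appears to save money as written but adds cost once the assay is counted.

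**4. Illustrative size.** Both inputs are assumptions and neither is in the documents. C is taken as USD 100 to 1,000. ΔQ is taken as 0.005 to 0.05, which corresponds to a constant utility difference of 0.01 to 0.10 over half a year (0.5 × 0.01 = 0.005; 0.5 × 0.10 = 0.05). Entries are C/ΔQ in USD per QALY.

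| C (USD) | ΔQ = 0.005 | 0.01 | 0.02 | 0.05 |
|---|---|---|---|---|
| 100 | 20,000 | 10,000 | 5,000 | 2,000 |
| 250 | 50,000 | 25,000 | 12,500 | 5,000 |
| 500 | 100,000 | 50,000 | 25,000 | 10,000 |
| 1,000 | 200,000 | 100,000 | 50,000 | 20,000 |

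The hundredfold spread shows that the size depends on the assumed inputs. The direction of the error in incremental cost does not.

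**The case against.** **The omission is inferred from silence.** No section says that the test cost is excluded; the only stated exclusion is the index surgical hospitalization. Section 10.6 defers details of these analyses to a study SAP that is not among the documents, and that SAP may add a price. Section 9 is also mainly about obtaining claims, so a fixed unit price need not appear there. This stands as a limit on wording: the claim is about what is specified here, not about what the analysts will finally do. It does not remove the point, because the cost sources are already set out and none can supply this item.

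**A reader might infer that the whole intervention is costed at zero.** The documents do not support that. Drug changes and visits prompted by the results can reach claims or self-report, since Section 6.7 leaves those costs with insurance. Who pays for consult notes or pharmacist and expert consultations (7.1) is not stated. Only the assay is shown to be unclaimed.

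**A reader might also scale the omitted cost up by the reciprocal of the actionable proportion** (18%, 30% or 40% in Table 9), because many must be tested to find one actionable patient. That would fit an analysis restricted to actionable phenotypes. The planned economic comparison is between study arms, so the shift is one test price per tested intervention participant.

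**The analysis is exploratory.** The synopsis labels it so, and the missing item is a per-person constant that could be added later. Both are true and limit the severity. Fixing the price rule in advance still matters, because a price chosen after results are known could be chosen to suit them.

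**Conclusion.** The point holds for the plan as specified in Sections 9 and 10.6. The assay cost reaches neither arm's total, so incremental payer cost is understated by C per tested intervention participant. The ICER is understated by C/ΔQALY if the QALY difference is positive, which nothing in the documents establishes. The bias favours testing and undercuts the stated reimbursement goal.

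The conclusion rests on three readings: that trial funding means no payer claim for the assay, that the utilization survey does not include it, and that the unseen SAP does not add it. No dollar figure can be drawn from the documents. Primary and secondary clinical endpoints, sample size and participants are unaffected. This is a correction that should be made before the economic analysis is run, not a threat to the trial's main results.

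**What to change.** In Sections 9.1 and 10.6 (Healthcare costs and Cost utility), and in the economic SAP:

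- Add a prespecified payer-level unit cost for the panel, with its source and in the 2021 price base, to every tested intervention participant, actionable or not. Enter zero for controls within the 6 months.
- Add it in dollars after the claims-based extrapolation and before any log transformation, so that it is neither rescaled nor lost.
- Say explicitly that it counts even though the assay precedes time zero. In chronic pain and depression, intervention follow-up starts at return of results (7.3).
- State how interpretation and consult costs are handled, and avoid double counting any that are billed and already in claims.
- Vary the test price in a sensitivity analysis and report the threshold price at which the conclusion changes.

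The cost is one added item and one sensitivity analysis, with no new participant data. The downside is that the reported cost-effectiveness becomes less favourable to testing.

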9.2 Data Collection

Data for this specialized analysis will come from these sources:

1. Participant report of healthcare utilization (e.g. emergency department, urgent care, office) for all participants, these will focus on high-cost items and/or items that are expected to be sensitive to the intervention
2. Medicare claims data for Medicare enrollees
3. Medicaid claims data for Medicaid enrollees

Participant reported visits: Participant reported assessment for health care utilization is previously described in section 7.3.

Medicare claims data: For Medicare enrollees in fee-for-service (FFS) plans or Medicare Advantage, clinical groups will ascertain Medicare claims data (Part A-D) directly from the Centers for Medicare and Medicaid Services (CMS).

Medicaid claims data: For Medicaid enrollees, clinical groups will ascertain claims data from their states' Medicaid agencies directly.

To ensure full adjudication, requests to Medicare/Medicaid for claims data will be timed to occur between 6-12 months after the end of the 6-months follow-up of the last enrolled patient. Claims data will also be requested for one year before trial enrollment up to 6 months thereafter.

The procedure for obtaining claims data will require a database linkage step – mapping the participant study ID to the Medicare/Medicaid identifiers. The data linkage will rely on social security number (SSN) or Medicare ID and date of birth (DoB), which can be collected in two possible ways:

1. Both SSN and/or Medicare ID and DoB are collected as part of the trial by the recruiting site
2. One or both variables are extracted from the medical record of the participating health center by a healthcare data security officer or the local equivalent, on behalf of the study team

For **2020-2024 Medicare data**, we will have three groups:(1) Clinical Trial Participants: To achieve our goals to understand the effects of a genotype-guided approach, we will have all Medicare beneficiaries who participated in the ADOPT PGx clinical trial and enrolled in the trial. (2) Controls- a standardized national cohort based on the 5% sample of beneficiaries who did not participate the clinical trial but had similar characteristics with beneficiaries who participate the clinical trial (received opioids or antidepressants). We will further require beneficiaries to have at least 2 months of Part D and at least 2 months of FFS in the year that they received the opioid or antidepressant. (3) Controls – a cohort of beneficiaries from Florida, New York, North Carolina, Tennessee, South Dakota, and Indiana (the states in which the clinical sites are located), pulled from the 100% sample, in which the beneficiaries did not participate the clinical trial but have similar characteristics with beneficiaries who participate the clinical trial received opioids or antidepressants). We will further require beneficiaries to have at least 2 months of Part D and at least 2 months of FFS in the year that they received the opioid or antidepressant. The clinical trial participants will be used to evaluate the effects of immediate vs delayed pharmacogenetic testing and genotype-guided pain or depression therapy on health care utilization, healthcare costs, and cost-effectiveness. We will further compare the Medicare beneficiaries among the trial enrollees to large random sample of beneficiaries who take pain medications to compare demographics and clinical characteristics to explore representativeness of the trial sample, making inferences about generalizability of the results.

For **2020-2024 Medicaid data**, we will have two groups: (1) Clinical Trial Participants: we will have all Medicaid beneficiaries who participated in the ADOPT PGx clinical trial and enrolled in the trial. (2) Controls- a cohort of beneficiaries from Florida, New York, North Carolina, Tennessee, South Dakota, and Indiana (the states in which the clinical sites are located), in which the beneficiaries did not participate the clinical trial but have similar characteristics with beneficiaries who participate the clinical trial received opioids or antidepressants). We will further require beneficiaries to have at least 2 months of FFS in the year that they received the opioid or antidepressant.

For the Controls for Medicare and Medicaid beneficiaries, waiver of consent forms and HIPPA waiver of authorization will be obtained as the analyses of health care utilization and costs are retrospective in nature. It will be impracticable to obtain authorization from this population sample as patient contact information is unavailable.

Costs imputation

The Medicare/Medicaid (M/M) claims will be used to impute healthcare utilization and costs for participants who are enrolled in other plans or not insured as follows. First, the subset of the study participants with both the participant reported set of medical encounters and M/M claims data will be identified. In this subgroup, claims data and self-report data will be used to derive extrapolation factors for total healthcare utilization and cost across all study participants. Additionally, for participants in other plans or uninsured, we will use M/M data to assign average cost to each of the self-reported items.

